9.3.2. Data Handling Conventions

9 3 2 1 General Methods

By-subject listings will be created for important variables from each eCRF module. Summary tables for continuous variables will contain the following statistics: N (number in population), n (number with data), mean, standard deviation, 95% confidence intervals (CIs) on the mean, median, minimum, and maximum. Summary tables for categorical variables will include: N, n, percentage, and 95% CIs on the percentage. Unless otherwise indicated, 95% CIs for binary variables will be calculated using the binomial distribution (exact method) and will be 2-sided. Data will be described and summarized by relevant treatment arm, analysis set, and timepoint. As appropriate, changes from baseline to each subsequent timepoint will be described and summarized by treatment arm. Similarly, as appropriate, the best change from baseline during the study will also be described and summarized by treatment arm. Graphical techniques (eg, waterfall plots, Kaplan-Meier curves, line plots) may be used when such methods are appropriate and informative.

Data from all sites will be pooled for all analyses. Analyses will be based upon the observed data unless methods for handling missing data are specified. If there is a significant degree of non-normality, analyses may be performed on log-transformed data or nonparametric tests may be applied, as appropriate.

9.3.2.2. Double-Blinded Portion of the Study Analyses

Efficacy and safety data collected during the blinded portion of Study GS-US-312-0117 will be presented in the following 2 groups:

- IDELA 300 mg BID: Subjects who have PD per IRC confirmation in Arm A of Study GS-US-312-0116 and subsequently enroll into Study GS-US-312-0117 to receive IDELA 300 mg BID during the double-blind portion of the study
- Placebo in Study GS-US-312-0116 + IDELA 150 mg BID in Study GS-US-312-0117: Subjects who have PD per IRC confirmation in Arm B of Study GS-US-312-0116 and subsequently enroll Study GS-US-312-0117 to receive IDELA 150 mg BID during the double-blind portion of the study

All analyses will be performed based on the data collected during the blinded-portion of the extension study. Time-to-event analyses will reference to the date of first treatment on this clinical trial (Study GS-US-312-0117). Similarly, evaluations of on-therapy changes will reference the baseline values obtained prior to treatment in this study. The baseline value used in each analysis will be the last (most recent) pre-treatment value. Analyses will be descriptive in nature and formal comparisons of outcomes in the 2 groups are not planned.

9.3.2.3. Open-Label Extension Study Analyses

GS-US-312-0117 will become an open-label study offering idelalisib 150 mg BID to GS-US-312-0116 subjects who were randomized to Arm B. Subjects randomized to Arm A will continue idelalisib at 150 mg BID. Efficacy and safety data collected during the primary and open-label extension studies will be presented in the following 4 groups:

- IDELA 150 mg BID: Subjects who are randomized to Arm A in Study GS-US-312-0116 and transition to Study GS-US-312-0117 during the open-label portion of the study to continue IDELA 150 mg BID
- Placebo in GS-US-312-0116 + IDELA 150 mg BID (open-label): Subjects who are randomized to Arm B in Study GS-US-312-0116 and transition to receive IDELA 150 mg BID during the open-label portion of the study
- IDELA 300 mg BID: Subjects who have PD per IRC confirmation in Arm A of Study GS-US-312-0116 and subsequently enroll Study GSUS-312-0117 to receive IDELA 300 mg BID during double-blind portion of the study
- Placebo in GS-US-312-0116 + IDELA 150 mg BID in GS-US-312-0117: Subjects who have PD per IRC confirmation in Arm B of Study GS-US-312-0116 and subsequently enroll Study GS-US-312-0117 to receive IDELA 150 mg BID during double-blind portion of the study.

Depending on the endpoints, analyses may be based on the combined data from both primary and extension studies or data from the extension study alone. Analyses will be descriptive in nature and formal comparisons of outcomes in the 4 groups are not planned. A separate statistical analysis plan will be created for the open-label portion of the study.

9.3.2.4. Calculation of Tumor Control and Patient Well-Being Variables

Tumor control assessments will be based on standardized IWCLL criteria {Cheson 2012, Hallek 2008}, as specifically modified for this study considering the pharmacology of idelalisib. The individual and composite endpoints of response and progression (considering changes in lymph node area, liver and spleen size, bone marrow, platelet counts, hemoglobin, neutrophil counts, and peripheral blood lymphocyte counts) will be determined. Tumor control will be documented at each assessment by response category (eg, CR, PR, SD, definitive PD, NE, ND) as defined for each response parameter, SPD value, percentage change in SPD values from baseline or nadir, date that response is first documented and date of definitive CLL progression.

The date of definitive CLL progression will be the timepoint at which progression is first identified by relevant objective radiographic or laboratory data. Because of the characteristic redistribution lymphocytosis that is expected with PI3Kδ inhibition, lymphocyte count will be ignored in the evaluation of progression. Changes in tumor status as provided by the investigator and changes in tumor status as adjudicated by the IRC (see Section 10.4.2) will be described. The findings of the IRC will be considered primary for analyses of all tumor control endpoints.

The following censoring conventions will be applied:

- PFS and DOR: Data from surviving, non-progressing subjects will be censored at the earliest of the time of initiation of antitumor treatment other than the study treatment or the last time that lack of definitive CLL progression was objectively documented. Data from subjects who have CLL progression or die after ≥2 consecutive missing tumor assessments will be censored at the last time prior to the missing assessments that lack of definitive CLL progression was objectively documented.
- OS: Data from surviving subjects will be censored at the last time that the subject was known to be alive.

9.4. Analysis Plan

9.4.1. Subject Disposition and Baseline Characteristics

A listing of all ITT analysis subjects will be generated to describe site, subject number, first screening date, first treatment date, allocated study drug assignment, actual study drug assignment, the longest duration of study drug treatment, and the reason for discontinuing study treatment. Available information on subjects who were screened or registered but not treated will be listed separately. A table will be created summarizing these categories in terms of number and percent for the ITT analysis set.

Subject baseline characteristics will be listed and summarized by treatment arm for the ITT analysis set. As appropriate for the specific variable, subject baseline characteristics acquired in Study GS-US-312-0116 will be referenced in Study GS-US-312-0117.

9.4.2. Efficacy Analyses

9.4.2.1. Time-to-Event Tumor Control and Survival Endpoints

PFS, DOR and OS will be described in the ITT analysis set using Kaplan-Meier methods by treatment group. Medians, ranges, and corresponding 95% CIs will be presented.

The Cox regression approach may be used to explore the influence of the primary study stratification factors and other baseline characteristics on PFS and OS. The stratification variables from the primary study and additional baseline subject characteristics may be included as covariates, focusing on those with expected prognostic significance.

9.4.2.2. Categorical Endpoints

Response rates, lymph node response rate, splenomegaly response rate, hemoglobin response rate, hepatomegaly response rate, ALC response rate, platelet response rate, hemoglobin response rate, and neutrophil response rate will be described. In the calculation of response rates, subjects who do not have sufficient baseline or on-study tumor assessment to characterize response will be included in the denominator. For all analyses, the corresponding 95% CIs will be presented.

The potential influence of subject baseline characteristics on response rates may be explored with multiple logistic regression modeling.

9.4.2.3. Continuous Endpoints

Changes in lymph node area and changes in performance status, PI3K/AKT/mTOR pathway activation, and plasma chemokines/cytokines will be assessed by treatment group. Both changes from baseline to each subsequent timepoint and best overall on-study changes will be analyzed using appropriate methods (eg, analysis of covariance [ANCOVA] or paired t-tests). Means and standard errors will be presented.

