
The timing of radiographic tumor assessments has been carefully considered. To avoid duplication, the CT scan documenting CLL progression in Study GS-US-312-0116 will serve as the baseline CT scan for Study GS-US-312-0117. Among patients receiving idelalisib in Phase 1b/2 studies who experienced a nodal response (≥50% regression in tumor area), such responses were observed with the first 16 week of therapy {Coutre 2011, Leonard 2011}; the planned timing of tumor assessments (at Weeks 8, 16, 24, 36, 48 and then every 12 weeks thereafter) in this study fits with this known timing of changes in lymph node size during idelalisib therapy. Scans at 8-week intervals during the first 24 weeks allow efficient documentation of response. During this period, early documentation of disease progression allows subjects who are not benefiting from study therapy to move rapidly to alternative

treatments. After 24 weeks on study or after 24 weeks cumulative treatment with idelalisib across Study GS-US-312-0116 and Study GS-US-312-0117, the reduction in the frequency of CT scans (to 12-week intervals) reduces the overall protocol burden for subjects while still allowing characterization of the expected median PFS in this trial. As outlined in Section 7.3, iodine-containing or gadolinium contrast material may be omitted in subjects for whom use of a contrast agent would be medically contraindicated.

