6.2.3. Visit 3 (Day 15) (Clinic Visit)

The procedures outlined in Table 6-3 will be performed at Visit 3 (Day 15 [±2 days]).

Table 6-3. Procedures and Assessments at Visit 3 (Day 15)

Assessment or Procedure	Explanation	
Pre-Dose Procedures and A	ssessments	
FACT-Leu	HRQL instrument (Appendix 2) to be administered before any other procedures are performed and before any study-related information is communicated to the subject	
EQ-5D	Health utility instrument (Appendix 4) to be administered after FACT-Leu but before any other procedures are performed and before any study-related information is communicated to the subject	
Adverse events	Recording of adverse events occurring since the initiation of the screening period	
Concomitant medications	Recording of concomitant medication use since the initiation of the screening period	
Performance status	Using Karnofsky performance status criteria (see Appendix 3)	
Oxygen saturation	To be assessed by pulse oximetry while subject is breathing room air	
Hematology	Including hematocrit, hemoglobin, erythrocyte count; absolute counts of leukocytes, neutrophils, lymphocytes, monocytes, eosinophils, basophils, platelet count	
Serum chemistry	Including sodium, potassium, chloride, glucose, urea, creatinine, calcium, phosphorus, total protein, albumin, ALT, AST, ALP, GGT, total bilirubin, LDH, uric acid, cholesterol, triglycerides	
Circulating cells	Including cells for analysis of PI3K/AKT/mTOR pathway activation and quantitation of absolute number of CD4+, CD5+, CD8+, CD16/CD56+, CD19+, and CD+20 cells by flow cytometry	
Biomarkers	Collection of plasma and serum for evaluation of circulating chemokines and cytokines	
Serum Igs	Including quantitative levels of IgA, IgE, IgG, and IgM	
Idelalisib pharmacokinetics	Recording of the date and actual clock time of the last prior subject self-administration of study drug (should be the prior evening dose). Pre-dose collection of plasma sample for idelalisib pharmacokinetics (with recording of the date and actual clock time of the date and actual clock time of blood collection)	
IWRS access	Access of IWRS to document subject visit	
Study Therapy Administra	tion	
Study drug administration	Study drug to be administered to the subject (with recording of the date and actual clock time of the study drug administration)	
Post-Therapy Procedures and Assessments		

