6.1.2.6. Best Percent Change in Lymph Node Area

The best percent change in SPD from baseline during the study will be summarized using descriptive statistics. The summary is based on subjects with sufficient baseline and on-study tumor measurements for the SPD calculation per IRC. The best percent change from baseline in SPD is defined as the largest decrease in tumor size during the study. The baseline SPD will be the last value collected prior to the baseline reference date for efficacy endpoints. Note that for subjects who only have increases in tumor size from baseline, the smallest increase will be considered as the best change from baseline in SPD. Waterfall plots of best on-study percent change in SPD will be provided for each treatment group using IRC data.

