6.1.2.10. Karnofsky Performance Status

The Karnofsky performance status scores and the change from baseline scores to each subsequent assessment will be summarized. The best change from baseline, defined as the highest change from baseline during the study, will also be summarized.

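### A paired t-test or confidence interval against zero is not calibrated for the best on-study change, which Protocol 9.4.2.3 allows; the exposure is the blinded portion and the pharmacodynamic endpoints

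*Protocol*

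**What the plan says.** Protocol 9.4.2.3 covers lymph node area, performance status, PI3K/AKT/mTOR pathway activation and plasma chemokines/cytokines. Its closing words on scope are "plasma chemokines/cytokines will be assessed by treatment group". Two summaries are to be analysed: the change at each later timepoint, and the best change. For both, "best overall on-study changes will be analyzed using appropriate methods (eg, analysis of covariance [ANCOVA] or paired t-tests". No reference value other than zero is named, and nothing allows for having picked the best of several visits.

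Protocol 9.3.2.1 asks that tables of continuous variables carry "95% confidence intervals (CIs) on the mean", and says that best change will be summarised by arm where appropriate. For the blinded portion, 9.3.2.2 fixes the comparator as a single value: "The baseline value used in each analysis will be the last (most recent) pre-treatment value".

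The SAP supplied covers the open-label portion only (SAP section 1). There, best nodal change gets descriptive statistics and waterfall plots (SAP 6.1.2.6: "The best percent change from baseline in SPD is defined as the largest decrease in tumor size during the study"). For Karnofsky status, SAP 6.1.2.10 says: "The best change from baseline, defined as the highest change from baseline during the study, will also be summarized". Neither section names a test. SAP section 9 leaves pharmacodynamics and biomarkers to a separate plan. SAP 6.2, on changes from the protocol's efficacy analyses, does not mention 9.4.2.3.

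**The concern.** A paired t-test takes a mean change of zero as its null. Best change is the most favourable of k post-baseline readings minus one baseline reading. With any within-subject variation, its mean is shifted in the favourable direction even if the subject's true level never moves. The test therefore asks whether the best of k readings equals baseline, not whether the measure changed on idelalisib. A 95% confidence interval on the mean best change carries the same fault without any t-test being run.

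At stake is how the within-group results will be read. Every group receives idelalisib and no formal comparison between groups is planned, so no control group would show the shift. Protocol 3.2.3 intends biomarker improvement to corroborate pharmacological activity, and 9.6 intends the extension data to support regulatory review of the primary study.

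**Working it through.** **The plan's own figures.** No alpha, power or error rate is stated for this analysis, so there is none to reproduce. The only design figure is the sample size in Protocol 9.5: 220 × 0.9 × 0.9 = 178.2, which matches the stated ~180. SAP 1.3 reports 161 enrolled, and SAP 3.5.1 gives N = 4 for the 300 mg group.

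**Inputs from the documents: number of readings, k, through Week 48**
- Lymph node area: scans "at Weeks 8, 16, 24, 36, 48 and then every 12 weeks thereafter", so k = 5 by Week 48.
- Pathway and chemokine/cytokine samples ("Collection of plasma and serum for evaluation of circulating chemokines and cytokines"): Visits 3, 4, 6 and 8-15, so k = 3 + 8 = 11.
- Karnofsky status: the same visits plus Visit 5, so k = 12.
- Baseline: one value.

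**Assumptions.** The documents give no within-subject SD, serial correlation or growth rate. The within-subject SD is set to 1 unit, with errors independent or AR(1) with correlation up to 0.95. The test is two-sided at 0.05, so the nominal rate of declaring improvement is 2.5%.

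**Method.** For subject i, d_i = max(e_i1, …, e_ik) − e_i0, with no true change. Test the mean of d against zero with t = mean(d) / (SD(d)/√n), over 2,000-4,000 simulated trials per cell.

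**Mean of d with no true change, independent errors:** 0.56 SD (k=2), 0.85 (k=3), 1.16 (k=5), 1.59 (k=11), 1.63 (k=12).

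**Probability of declaring improvement with no true change, independent errors**

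| k | n=4 | n=10 | n=20 |
|---|---|---|---|
| 2 | – | – | 45% |
| 5 | 26% | 77% | 98-99% |
| 11 | 46% | 97% | 100% |
| 12 | – | 98% | 100% |

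**Sensitivity of the stable case**
- AR(1) correlation 0.95: k=5 gives 90% at n=20 and 99.6% at n=40; k=11 gives 99.8% at n=20.
- Karnofsky in 10-point steps, SD 5: k=5 gives 90% at n=20; k=12 gives 100% at n=20.
- A random 1 to 11 visits per subject: 94% at n=20 and 99.9% at n=40.

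**When the measure drifts the wrong way**
- Constant decline of 0.5 SD at every visit, n=30: 83% (k=5) and 100% (k=12) still declare improvement.
- Decline building up by 0.5 SD per visit: about 2%. By 1 SD per visit: 0%.
- Nodal area, 5 scans, n = 20 to 90. No growth: 95-100%. Growth of 5% per 8 weeks: 0.5-1.7% at a measurement CV of 10%, and 26-74% at a CV of 20%. Growth of 10% or more: about 0-1%.

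**Control.** The same test on the change at one fixed visit declares improvement in 2.2-2.8% of trials for n = 4 to 90, so its size is nominal.

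**ANCOVA** was not simulated. Within one group, the baseline-adjusted mean evaluated at the average baseline equals the raw mean best change, so it carries the same shift.

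**The case against.** The strongest reply is that the plan does not commit to this test. The methods are introduced as examples, in one sentence that covers fixed-timepoint changes as well. No alpha or decision rule is attached, the analyses are declared descriptive, and the sample size rests on no hypothesis. The supplied SAP names no test for best nodal or Karnofsky change. A separate plan may do the same for the blinded portion, and the biomarker plan may do so for the pharmacodynamic endpoints; neither was supplied. All of this stands, and it limits the weight of the point. It does not make either named method suitable for best change, and no supplied text withdraws them for the blinded portion or the pharmacodynamic endpoints.

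Two stronger readings are tempting and are not supported:
- A reader might infer that an inert drug would almost always appear effective. Subjects in the blinded portion enter at confirmed progression, and Protocol 3.2.1 describes untreated nodal disease as steadily growing. Under such growth the test may rarely or never declare improvement in lymph node area. Subjects also leave at progression, so 5 or 12 readings each is an upper case, and one blinded group has only 4 subjects.
- A reader might infer that these are the only inferential results on the endpoints. The same sentence of 9.4.2.3 already provides for change at each timepoint, and 9.4.4.1 allows between-study comparisons in Arm B.

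**Conclusion.** The point holds in limited form. A test or confidence interval against zero is not calibrated for best on-study change, and the protocol permits both. For a stable measure with 5 or more readings and 20 or more subjects, improvement is declared in 90-100% of simulated trials with no true change, against a nominal 2.5%. In very small groups or with few visits the rate is lower but still well above nominal. With accumulating worsening it can fall below nominal. The error therefore depends on visit count, noise and drift, and a reader of the result could not tell which case applies.

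These rates rest on the assumed error structure and growth rates and on two-sided 0.05. That the mean best change is not zero under no change needs only some within-subject variation and more than one reading. No success criterion hangs on the analysis, so this is a correction that should be made rather than a threat to the study's main conclusions.

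**What to change.** In Protocol 9.4.2.3, restrict paired t-tests and ANCOVA to change from baseline at prespecified scheduled visits, or use a repeated-measures model over those visits. Present best on-study change descriptively only (median, range, waterfall plot), with no p-value and no confidence interval against zero, and exempt it from the interval on the mean in 9.3.2.1. Carry the same rule into the biomarker analysis plan and any plan for the blinded portion.

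The cost is wording: no new data are needed, and fixed-timepoint analysis is already planned. The downside is that nominally significant best-change results would no longer be reported.

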9.4.2.4. Health-Related Quality of Life and Performance Status

The FACT-Leu questionnaire data will be scored and processed according to the user manual. Missing items in a subscale will be imputed consistent with the user manual instructions. Data collected from the FACT-Leu instrument will not be reconciled with adverse event or laboratory data or with EQ-D5 findings.

As a baseline, the last value obtained prior to receiving the first idelalisib dose of 150 mg and 300 mg will be used, depending on the treatment group assigned.

The mean and change from baseline in mean scores to each subsequent assessment will be summarized for the FACT-Lym subscale and composite scores. The best change from baseline during the study, defined as the highest positive value among all post-baseline visits minus the baseline value, will also be summarized.

9.4.3. Exposure and Safety Analyses

9.4.3.1. Treatment Administration and Study Drug Compliance

Descriptive information will be provided by treatment arm regarding the number of doses of study therapy prescribed, the total number of doses taken, the percent of expected doses taken, the number of days of treatment, and the number and timing of prescribed dose reductions and interruptions.

Study drug compliance will be described by treatment arm in terms of the proportion of study drug actually taken based on returned pill count relative to the amount that was dispensed (taking into account physician-prescribed reductions and interruptions).

9 4 3 2 Idelalisib Plasma Concentrations

Bioanalytical analyses will performed independently so that the study team and investigators will not have knowledge of data from individual subjects. Idelalisib plasma concentrations immediately pre-dose and at 1.5 hours after administration of the dose of study drug at each relevant clinic visit will be summarized by treatment and visit using descriptive statistics.

